4.0 Eligibility

Identify the subject population being evaluated by the protocol: All study participants will be healthy volunteers. Out of the sample recruited for this research, two groups will be formed based on the smoking status: Healthy non-smokers and healthy smokers. The criteria to separate the two groups is listed in Section 4.1 Inclusion Criteria.

Indicate the source of subjects: Study participants will be recruited from the general population using electronic media (ex: Craigslist), flyers, newspaper advertisements and word-of mouth referrals.

Identify who will assess and determine subject eligibility: Research staff (postdoctoral fellow(s) and research coordinator(s)) will assess eligibility criteria based on a detailed flowsheet (i.e. checklist) created specifically for this study. All research staff will be trained by the PI on assessing inclusion/exclusion criteria. The record of this training will be kept on file in the PI's laboratory. Study PI will sign off on all study participants who passed the screening session as the final approval of subject's entry into the study.

Indicate how and where eligibility will be documented: After completing each step of the flowsheet, the coordinator/postdoctoral research fellow will place time of completion and his/her initials. The PI will document approving participants for study participation on the flowsheet.

Attach an eligibility checklist to the protocol: Eligibility will be documented on the "Session Flowsheet", which is attached to this application. It is also listed in Sections 4.1 and 4.2 below.

4.1 Inclusion Criteria

- Age between 21-40 years
- Smokers only: Smoke at least 10 cigarettes daily (verified by carbon monoxide concentrations greater than 10 ppm).
- Non-smokers only: No self-reported cigarette use in the past 1-year period.
- Non-smokers only: Carbon monoxide concentration < 6 ppm.
- Normal vitals (blood pressure < 120/80 mmHg; heart rate between 60 and 100 bpm, body temperature <37 °C)
- Point-of-care (POC) blood glucose between 70 and 140 mg/dL
- Body mass index between 18.5 and 30 kg/m²

4.2 Exclusion Criteria

- Use of non-cigarette tobacco products, e-cigarettes, or smoking cessation treatment
- Positive urine drug screen test
- Current pregnancy (urine test-verified) or lactation, or a plan to become pregnant
- Breath Alcohol Concentration >0.00%
- Shipley IQ test <80
- Hyposmic or anosmic individuals (identifying less than 10 of 12 smells correctly)
- Abnormal physical exam of the nares
- Lifetime DSM-5 Axis 1 disorder (except anxiety and depression)
- Current DSM-5 Axis depression or anxiety disorder
- Over-the-counter or prescription psychotropic medications (confirmed by PI upon screening)
- Use of any medications administered intranasally
- Allergies to any ingredients in intranasal insulin or placebo

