5.0 Subject Enrollment

Describe screening and enrollment: The telephone number and email of the CEDAR lab will be included in the advertisement. Once participants contact the lab, they will complete an initial screening survey (please see document "Initial Survey"). Study participants will have the option of completing the survey either electronically (via REDCap link) or by calling in. In the case of a phone call, study coordinator will enter participant responses into REDCap for determination of eligibility. Participants passing the "Initial Survey" will be scheduled for an in-person screening. The document "Screening Flowsheet" outlines the procedures which will be completed at the in-person screening to determine eligibility as outlined in Section 4.1 and 4.2.

Describe from where subjects will be recruited and any advertising or recruitment materials that will be used: Study participants will be recruited from the general population using electronic media (ex: Craigslist), flyers, newspaper advertisements and word-of mouth referrals. The advertising materials will include hard copy posters and Craigslist advertisement. Copies of both are attached to this application.

Describe what happens with screen failures and any data obtained from screen failures: Data gathered from participants failing the screening criteria will be kept with all study documentation, following which it will be shredded with the remaining study documentation. The reason the documentation will be kept is in the event the same subject returns with information different from what he/she reported previously. In this event, we will be able to compare responses and optimize subject protection and study integrity.

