Describe the methods to minimize coercion and undue influence on the subjects: The consent procedure is detailed according to processes established in the Code of Federal Regulation and University of Illinois Institutional Review Board. Each research coordinator and postdoctoral research fellow will be trained by the PI and will complete the checklist (included in the "Screening Flowsheet" document). Study participants will be given ample time to review the form. The consent procedure will be carried out in a private and quiet setting. Prior to initiating the procedure, the person consenting will ensure that the individual is adult, able to read and understands the English language. The most recent version of the consent form will be used. The individual obtaining the consent will summarize each section of the consent. Study participants will be told the following: "Take as much time as you need to read the entire consent form. Please inform me when you are done reading the form so I may answer any questions you have." All the questions the subject had will be written on the coordinator flowsheet. The signed informed consent copy will be given to study participant.

Describe the procedures to separate clinical responsibilities and influence from research responsibilities and influence: This research study does not recruit patients; hence, there are no clinical responsibilities.

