6.0 Study Design and Procedures

List any collaborating sites where human subjects research will be performed, and describe the role of those sites and collaborating investigators in performing the proposed research (if applicable): This study will be only conducted at University of Illinois. Study space will be rented at Center for Clinical and Translational Science. In addition, UIC nurse will be responsible for performing nasal examination and collecting blood samples. Study personnel – working out of the PI's laboratory - will ensure regulatory compliance, recruit participants, as well as collect and analyze the data. The PI's lab is located on the first floor of UIC College of Pharmacy. Study materials, equipment and all paper copies will be locked in the office of research staff affiliated with the study.

Describe the study design. The description should be capable of meeting the study objectives: This is a two group, two session study. The only eligibility criteria separating the two groups is the smoking status, otherwise the study population will consist of healthy volunteers. Following successful completion of the "Initial Survey", study participants will be scheduled for a 3-hr In-Person Screening visit. At the in-person screening, participants will 1. be consented, 2. provide urine and breath samples, 3. complete surveys, and 4. receive study instructions. After the completion of the "In-Person Screening", study participants will be scheduled for two study sessions, separated by a minimum of 1 week. During the study session, in random order, study participants will receive either intranasal insulin (60 IU) or placebo. This is a cross-over study –participants receiving intranasal insulin will receive placebo next, and vice-versa. Please refer to Table 1 for a summary of the study

session. The sessions will be identical, other than participants receiving intranasal insulin or placebo in random order.

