6.1 Procedures and Assessments

Provide a thorough description of all study procedures, assessments and subject activities in a logical and sequential format. Indicate what study activities happen when and where, including, when applicable, a study schedule that notes number and length of study visits for subjects.

Table 3. Outline of Study Session	
TIME	PROCEDURE
8:00-8:30	Determination of session eligibility (urine and breath tests)
8:30-8:50	Nicotine gum break (smokers), generic chewing gum break (non-smokers)
8:50-9:00	Nicotine blood sample
9:00-9:05	POC glucose check
9:05-9:15	Nares exam
9:15-10:00	Relaxation phase (both smokers and non-smokers)
10:00-10:06	Spray administration
10:10-10:30	Equipment setup
10:30-11:40	Go-No/Go task
11:40-11:45	Olfactory function test
11:45-12:00	Discharge procedure (POC measurement)

Study session will begin at 8:00 AM. First, the research coordinator will ensure that the lab has a signed consent form on file from the participant. Smokers will be instructed to smoke the normal amount of cigarettes they usually smoke upon waking prior to each session, then refrain from smoking until the end of the session. For example, if they usually smoke 2 cigarettes upon waking, they will be instructed to smoke 2 cigarettes prior to the first session (30 minutes upon waking) and 2 cigarettes prior to the second session (30 minutes upon waking). Participants will be asked if they have had breakfast. If they did not eat breakfast that morning, research coordinator will give them a granola bar and re-emphasize the importance of eating breakfast. Next, from 8:00 AM to 8:30 AM, urine and breath samples will be obtained by the study coordinator, for verification of absence of alcohol intake. A urine sample will be obtained to rule out illicit drug intake and pregnancy. See Section 6.2 Specimen Considerations for more information on urine sample collection and analysis protocol.

At 8:30, smokers will take a 20-minute nicotine chewing gum (Nicorette gum, 4mg) break, and non-smokers will take a 20-minute generic, non-nicotine chewing gum break. As per the instructions given by Nicorette, smokers will be instructed chew the gum slowly until they experience a tingling sensation, then to place the gum between their cheek and gum until the tingle subsides and repeat until most of the tingle is undetectable. Non-smokers will be instructed to chew the generic gum at their own pace.

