6.3 Drug Product Considerations

Name and description of product: The drug substance used for preparation of the final drug product will be bulk Novolin R. Novolin R is a sterile, clear, aqueous, and colorless solution that contains human insulin (rDNA origin) 100 units/mL, glycerol 16 mg/mL, metacresol 3 mg/mL, zinc chloride approximately 7 mcg/mL and water for injection. The pH is adjusted to 7.4. Hydrochloric acid 2N or sodium hydroxide 2N may be added to adjust pH. Novolin R vials are latex-free. The drug substance is being purchased from McKesson. The placebo utilized in this study is 14% sodium chloride in sterile water.

Route of administration, dosing, dosage regimen and duration: Intranasal insulin will be prepared by University of Illinois Hospital and Health Sciences System Investigational Drug Service. The service is located in the Hospital Pharmacy and contains a segregated compounding area with a biological safety cabinet (BSC). The drug product will be compounded in the BSC using aseptic technique. The pharmacist or a pharmacy technician designee will prepare the requisite drug product following personnel hand hygiene and garbing procedures according to USP<797>. Aero Pump nasal spray system is manufactured in ISO Class 7 environment, hence sterilization of the system prior to compounding procedure will not be necessary. Aero Pump and Novolin R vial will be placed into the BSC. A volume of 3.3 mL Novolin R will be withdrawn using a set of sterile needle and syringe followed by emptying the contents of the syringe into the AeroPump glass bottle. The bottle will then be capped with AeroPump nasal spray. Finally, sterile gauze will be sprayed with sterile IPA following which 20 sprays will be pumped into the gauze for the purpose of priming the final drug product.

Placebo will be prepared using the aseptic technique as described for intranasal insulin. The pharmacist or a pharmacy technician designee will transfer 2.7 mL of sterile water and 4 mL of sterile 23.4% NaCl solution into a sterile container with 10 mL capacity. A volume of 3.3 mL of 14% NaCl

solution will be aseptically placed in the Aeropump spray as describeda. The final step will be the same priming procedure as for insulin spray.

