The directions for spray administration will be one spray in each nostril every 3 minutes for the total of 6 sprays delivered over 6 minutes. AeroPump delivers 0.1 ml of liquid per spray. Since the concentration of insulin in Novolin R is 100 IU/mL, six sprays will deliver the 60 IU dose. Aero Pump and Novolin R vial will be placed into the BSC. A volume of 3.3 mL Novolin R will be withdrawn using a set of sterile needle and syringe followed by emptying the contents of the syringe into the AeroPump glass bottle. The bottle will then be capped with AeroPump nasal spray. Finally, sterile gauze will be sprayed with sterile IPA following which 20 sprays will be pumped into the gauze for the purpose of priming the final drug product.

Placebo will be prepared using the aseptic technique as described in the above paragraph. The pharmacist or a pharmacy technician designee will transfer 2.7 mL of sterile water and 4 mL of sterile 23.4% NaCl solution into a sterile container with 10 mL capacity. A volume of 3.3 mL of 14% NaCl solution will be aseptically placed in the Aeropump spray as described in the “Drug Product” paragraph. The final step will be the same priming procedure as for insulin spray.

Describe how any adverse events or serious adverse events will be handled: Section 11.0 describes in detail study procedures which will be implemented to 1. Ensure thorough and accurate collection of AEs and UPs, 2. Timely reporting to the Institutional Review Board, and 3. Follow-up and resolution of all potential AEs and UPs.

List/describe the expected adverse events based on the product label: Expected adverse events from an investigational study conducted with intranasally administered Novolin R (IND#120700) are listed below:

- Local (nasal): anosmia, nasal irritation, local tissue damage
- Cognitive: confusion, visual disturbances
- Others: sweating, shaking, hunger, tingling sensation around the mouth

Expected adverse events from the product label for Nicorette gum are listed below (Nicorette Informational Pamphlet, 2017):

- Central nervous system: Depression, dizziness, headache, insomnia, lack of concentration, nervousness, pain, paresthesia
- Dermatologic: Diaphoresis
- Gastrointestinal: Aphthous stomatitis, constipation, diarrhea, dysgeusia, dyspepsia, flatulence, gingival hemorrhage, glossitis, hiccups, nausea, sialorrhea, stomatitis, tooth enamel damage (abrasions), xerostomia
- Dermatologic: Skin rash
- Hypersensitivity: Hypersensitivity reaction

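### The allergy exclusion in section 4.2 covers the two nasal sprays but not the 4 mg nicotine gum that every smoker is scheduled to chew at both sessions

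*Combined protocol and SAP*

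**What the plan says.** Section 4.2 ends its list of exclusions with "Allergies to any ingredients in intranasal insulin or placebo". Neither 4.1 nor 4.2 has another allergy criterion, and 4.3 adds nothing on the subject.

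Section 6.3 settles what placebo means: "The placebo utilized in this study is 14% sodium chloride in sterile water".

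Section 6.1 adds a third product for the smoker group. At 8:30, "smokers will take a 20-minute nicotine chewing gum (Nicorette gum, 4mg) break"; non-smokers chew a generic gum without nicotine. Section 6.0 says of the two visits: "The sessions will be identical, other than participants receiving intranasal insulin or placebo in random order". The nicotine gum is therefore scheduled at both.

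Section 6.3 then introduces the gum's adverse events with "Expected adverse events from the product label for Nicorette gum are listed below", and hypersensitivity reaction is one of the entries.

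On how eligibility is decided, section 5.0 says that the Screening Flowsheet "outlines the procedures which will be completed at the in-person screening to determine eligibility as outlined in Section 4.1 and 4.2". Section 4.0 adds a last step: "Study PI will sign off on all study participants who passed the screening session as the final approval".

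**The concern.** The protocol treats allergy to an administered product as a reason for exclusion, but applies this only to the sprays. The gum is also given by the study, is a source of adverse events on the protocol's own account, and has hypersensitivity on its label list.

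The protocol already uses eligibility to control the gum's risks in one respect. Section 7.0 keeps pregnant and nursing women out because of nicotine's possible side effects. The allergy line was not extended in the same way.

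What is at stake is an avoidable exposure. A smoker who knows of an allergy to a gum ingredient meets no written exclusion on that account and is scheduled to receive the product twice. Section 7.0 expects no benefit to participants, and section 11.0 states that the study is not minimal risk, so a foreseeable risk that is cheap to screen for should be covered by a stated criterion.

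**Working it through.** The plan gives no figure to reproduce on this point. The check is a comparison of sections, with a few counts.

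**1. Does any criterion cover gum allergy?**
- Section 4.1 has 7 criteria and section 4.2 has 12: 7 + 12 = 19.
- Criteria on allergy: 1, the last line of 4.2.
- Criteria that mention the gum: 0.
- The nearest is the 4.2 exclusion for smoking cessation treatment. It concerns use of such products, not allergy to them.

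**2. Could the word placebo include the gum?** No. Sections 2.0 and 6.3 both define placebo as a 14% sodium chloride solution in sterile water, delivered as a spray.

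**3. How much of a smoker's exposure does the allergy line cover?**

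| Product scheduled for a smoker | Source | In the 4.2 allergy line? |
|---|---|---|
| Insulin spray, one session | 6.0, 6.3 | Yes |
| Placebo spray, one session | 6.0, 6.3 | Yes |
| Nicotine gum 4 mg, both sessions | 6.0, 6.1 | No |

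Two of the three products are covered. Gum administrations per smoker: 1 per session × 2 sessions = 2. With the 60 participants per group planned in section 12.0, that is 60 × 2 = 120 scheduled nicotine gum administrations among completers. This counts exposures, not expected reactions.

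**4. Is the hazard the protocol's own?** Yes. Hypersensitivity reaction is in the section 6.3 list taken from the Nicorette label. Smokers must smoke at least 10 cigarettes daily (4.1) and so already take in nicotine. The concern is therefore mainly the gum's other ingredients, which the documents do not list.

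**5. Does another stated step close the gap before exposure?**
- *Screening Flowsheet.* Section 5.0 ties it to 4.1 and 4.2, which do not mention the gum. The form itself is not in the documents.
- *Medication and Health Review.* The data collection table in section 8.0 marks it as used for eligibility, but its content is not described.
- *Consent.* Section 5.0 says "The individual obtaining the consent will summarize each section of the consent". Gum allergy is not named.
- *Health questions* (13.2) and *investigator sign-off* (4.0). Both are general.
- *Adverse event questioning.* Section 11.0 names the gum, but the questionnaire is completed at the end of the session. In the section 6.1 timetable the gum break starts at 8:30 and discharge at 11:45, which is 3 hours 15 minutes later. This is monitoring after exposure, not screening.

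**The case against.** The strongest reply is that the gap may exist only on paper. Staff assess eligibility from a detailed checklist attached to the application but not included in the documents. That checklist may well go beyond 4.1 and 4.2: section 8.0 marks a Hearing Test as used for eligibility, although neither list has a hearing criterion. A participant who knows of an allergy would also have to pass through the Medication and Health Review, the health questions, the consent discussion (which section 1.0 says will cover anticipated risks of study drugs) and the investigator's sign-off without anyone picking it up. This stands as a limit on the point: the documents do not show that screening omits the question. It does not remove the point, because none of these steps is stated to cover gum allergy, and the written criteria are what staff are trained to apply.

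Second, the hazard rests on one label term with no frequency or severity. That is correct, and it is why no probability is given and the point is graded low.

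Third, if non-nicotine ingredients are the worry, the non-smokers' generic gum should be treated alike. This has some force. The difference is that the documents list a hypersensitivity risk for the Nicorette gum and none for the generic gum, so covering the latter is optional.

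Fourth, a reaction at the first session would be recorded and reviewed before the second, at least a week later, and the study nurse sees the participant soon after the gum break. Both may limit the consequences, but neither prevents the first exposure.

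**Conclusion.** The concern holds for the written criteria. Applied as worded, sections 4.1 and 4.2 do not exclude a smoker with a known allergy to a nicotine gum ingredient, and the schedule then gives that person the gum at both sessions. Keeping such a person out depends on forms outside the documents or on individual judgement.

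The point is minor. It concerns participant safety only and has no effect on the sample size, the primary analysis or the insulin-placebo comparison. The conclusion rests on the protocol text alone and assumes nothing about how common gum-ingredient allergy is or about what the unseen flowsheet asks. If the flowsheet already has the question, only the wording of 4.2 needs correcting.

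**What to change.** Extend the last line of section 4.2 so that it also excludes allergy to any ingredient of the nicotine gum given to smokers. Then check whether the Screening Flowsheet already asks about this, and add one question only if it does not. Naming the non-smokers' generic gum as well is optional.

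The cost is one phrase in the protocol, at most one screening question, and an occasional extra screen failure.

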4.3 Excluded or Vulnerable Populations

Describe specifically and state the justification for any vulnerable populations (i.e., minors) or any excluded populations (i.e., non-English speaking subjects): Vulnerable populations will not be included in the study. Participants who don't speak English are not included in the study because the questionnaires and study instructions have been developed in the English language.

5.0 Subject Enrollment

Describe screening and enrollment: The telephone number and email of the CEDAR lab will be included in the advertisement. Once participants contact the lab, they will complete an initial screening survey (please see document "Initial Survey"). Study participants will have the option of completing the survey either electronically (via REDCap link) or by calling in. In the case of a phone call, study coordinator will enter participant responses into REDCap for determination of eligibility. Participants passing the "Initial Survey" will be scheduled for an in-person screening. The document "Screening Flowsheet" outlines the procedures which will be completed at the in-person screening to determine eligibility as outlined in Section 4.1 and 4.2.

Describe from where subjects will be recruited and any advertising or recruitment materials that will be used: Study participants will be recruited from the general population using electronic media (ex: Craigslist), flyers, newspaper advertisements and word-of mouth referrals. The advertising materials will include hard copy posters and Craigslist advertisement. Copies of both are attached to this application.

Describe what happens with screen failures and any data obtained from screen failures: Data gathered from participants failing the screening criteria will be kept with all study documentation, following which it will be shredded with the remaining study documentation. The reason the documentation will be kept is in the event the same subject returns with information different from what he/she reported previously. In this event, we will be able to compare responses and optimize subject protection and study integrity.

Describe the methods to minimize coercion and undue influence on the subjects: The consent procedure is detailed according to processes established in the Code of Federal Regulation and University of Illinois Institutional Review Board. Each research coordinator and postdoctoral research fellow will be trained by the PI and will complete the checklist (included in the "Screening Flowsheet" document). Study participants will be given ample time to review the form. The consent procedure will be carried out in a private and quiet setting. Prior to initiating the procedure, the person consenting will ensure that the individual is adult, able to read and understands the English language. The most recent version of the consent form will be used. The individual obtaining the consent will summarize each section of the consent. Study participants will be told the following: "Take as much time as you need to read the entire consent form. Please inform me when you are done reading the form so I may answer any questions you have." All the questions the subject had will be written on the coordinator flowsheet. The signed informed consent copy will be given to study participant.

Describe the procedures to separate clinical responsibilities and influence from research responsibilities and influence: This research study does not recruit patients; hence, there are no clinical responsibilities.

